8.1.3. Definitions of Baseline and Change from Baseline

Baseline value is defined as the last non missing measurement before administration of LOXO-305 in each treatment period.

 Part 1

In general, baseline for Part 1 refers to the pre-dose value collected on Day 1 period 1 and Day 12. For laboratory tests, baseline is the value collected on Day -1 period 1 and Day 11 period 2.

Part 2

In general, baseline for Part 2 refers to the pre-dose value collected on Day 1 period 1, Day 8 period 2 and Day 17 Period 2.

If the date/time of the value is incomplete or missing, it will be excluded from the baseline calculation, unless the incomplete date/time indicates the value was recorded prior to dosing of LOXO-305 in each period.

Individual changes from baseline will be calculated by subtracting the individual subject's baseline value from the value at the timepoint. The mean change from baseline will be defined as the mean of the individual changes from baseline for all subjects.

See Section 8.1.2 for more detail on handling repeat and unscheduled readings in the calculations.

8.2. Subject Disposition and Population Assignment

Subject disposition and population assignment will be listed.

A summary table by treatment sequence will be provided, based on the all subjects population.

8.3. Screening Demographics and Baseline Characteristics

The screening demographics and baseline characteristics including age, sex, race, ethnicity, height, body weight, and body mass index will be listed.

A summary table by treatment sequence will be provided, based on the safety population.

8.4. Prior and Concomitant Medication

Prior medication will be defined as medication that ends prior to the first dose of LOXO-305. Concomitant medication will be defined as medication that starts during or after the first dose or starts but does not end prior to the first dose.

Prior and concomitant medications will be coded using the World Health Organization Drug Dictionary (WHODrug) Global, Format B3, Version September 2019. Prior and concomitant medications will be listed.

8.5. Pharmacokinetic Assessments

8.5.1. Pharmacokinetic Analysis

The following PK parameters will be determined where possible from the plasma concentrations of LOXO-305 using non-compartmental methods performed using Phoenix WinNonlin (Certara USA, Inc.) version 8.1 or higher:

Parameter	Definition
AUC ₀₋₂₄	area under the concentration-time curve from Hour 0 to 24 hours postdose, as calculated by the linear trapezoidal rule for increasing and decreasing concentrations (for Day 1 and Day 8 of Part 2 PK only)
AUC _{0-t}	area under the concentration-time curve (AUC) from Hour 0 to the last measurable concentration, calculated using the linear trapezoidal rule for increasing and decreasing concentrations
AUC _{0-inf}	AUC extrapolated to infinity, calculated using the formula:
	$AUC_{0-inf} = AUC_{0-t} + \frac{C_t}{\lambda_z}$
	where C_t is the last measurable concentration and λ_Z is the apparent terminal
	elimination rate constant
%AUC _{extrap}	percentage extrapolation for AUC _{0-inf} (except for Part 2 Day 8)
C _{max}	maximum observed plasma concentration
t _{max}	time to maximum observed plasma concentration
λz	apparent terminal elimination rate constant, where λ_z is the magnitude of the
	slope of the linear regression of the log concentration versus time profile
	during the terminal phase; additionally, the number of points used to estimate
	λ_z will be presented in a listing (wherever possible)
$t_{1/2}$	apparent terminal elimination half-life (whenever possible),
	where $t_{1/2} = natural \log (ln)(2)/\lambda_Z$
CL/F	apparent systemic clearance (except for Part 2 Day 8)

Additional PK parameters may be determined where appropriate. The number of points used to estimate λ_Z , the lower and upper points used in estimation, λ_Z span ratio, and the adjusted coefficient for determination of exponential fit (R² adjusted) will be presented in a listing.

The PK analysis will, where possible, be carried out using actual postdose times recorded in the raw data. If actual times are missing, nominal times may be used with sponsor approval.

Concentrations are used as supplied by the analytical laboratory for PK analysis. The units of concentration and resulting PK parameters, with amount or concentration in the unit, will be presented as they are received from the analytical laboratory.

No value for λ_Z , AUC_{0-inf}, CL/F, or t¹/₂ will be reported for cases that do not exhibit a terminal log linear phase in the concentration-time profile. The PK sampling to 24 hours on Day 8 in Part 2 may not be sufficient for calculation of several λ_Z -dependent PK parameters.

No PK parameters will be calculated for subjects with 2 or fewer consecutive timepoints with quantifiable concentrations.

 C_{max} and t_{max} will be obtained directly from the plasma concentration-time profiles. For multiple peaks, the highest postdose concentration will be reported as C_{max} . In the case that multiple peaks are of equal magnitude, the earliest t_{max} will be reported if possible.

8.5.1.1. Criteria for Handling Concentrations Below the Limit of Quantification in Pharmacokinetic Analysis

Concentration values that are below the limit of quantification (BLQ) will be set to zero, with defined exceptions as follows;

- Any embedded BLQ value (between 2 quantifiable concentrations) and BLQ values following the last quantifiable concentration in a profile will be set to missing for the purposes of PK analysis.
- If there are late positive concentration values following 2 BLQ concentration values in the apparent terminal phase, these values will be evaluated. If these values are considered to be anomalous, they will be set to missing.
- If an entire concentration-time profile is BLQ, the profile will be excluded from the PK analysis.
- If a Period 1 predose concentration is missing, it may be set to 0 (for PK analysis only) by default within the Phoenix WinNonlin software. Handling of missing predose values in Period 2 will be assessed on a case by case basis.

8.5.1.2. Criteria for the Calculation of an Apparent Terminal Elimination Rate Constant and Half-Life

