1.4.2. Pharmacokinetics

As of 25 October 2019, preliminary steady-state PK data (Day 8 of Cycle 1) were available from 25 patients enrolled in LOXO-BTK-18001. These data demonstrate that LOXO-305 is absorbed after oral administration with a median time to maximum observed concentration (t_{max}) of approximately 2 hours and low clearance (Table 1).

Although the plasma half-life could not be calculated with certainty because of the limited sampling interval (0 to 8 hours), it appears to be approximately 18 hours. Steady-state PK parameters of LOXO-305 in these cancer patients are presented in Table 1. Following administration of the 100 mg QD, 150 mg QD, or 200 mg QD, mean unbound trough plasma levels of LOXO-305 exceeded the concentration required for 90% inhibition (IC₉₀) of the C481S mutant of BTK in vitro.

 Table 1: Preliminary Pharmacokinetic Parameters of LOXO-305 in Patients with Cancer (Study LOXO-BTK-18001)

Dose (mg)	Ν	C _{max} (ng/mL)	t _{max} (h)	AUC ₀₋₂₄ (ng·h/mL)	CL/F (L/h)	t _½ (h)
25 mg (QD)						
50 mg (QD)						
100 mg (QD)						
150 mg (QD)						
200 mg (QD)						

Abbreviations: AUC₀₋₂₄ = area under the concentration-time curve from Hour 0 to 24 hours postdose; CL/F = apparent oral clearance; C_{max} = maximum observed plasma concentration, CV = coefficient of variation; N = number of patients; QD = once daily; $t_{1/2}$ = apparent terminal elimination half-life; t_{max} = time to maximum observed concentration. Mean (CV%) data are presented for C_{max} , AUC₀₋₂₄, CL/F, and $t_{1/2}$; median (minimum-maximum) data are presented for t_{max} . Data cutoff date: 25 October 2019.

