8.5.1.3. Calculation of AUC

The minimum requirement for the calculation of AUC will be the inclusion of at least 3 consecutive plasma concentrations above the lower limit of quantification (LLOQ), with at least one of these concentrations following C_{max} .

For any partial AUC determination (eg, AUC_{0-24}), nominal time will generally be used for the end of the interval. Actual times for partial AUC intervals may be used at the discretion of the pharmacokineticist.

 AUC_{0-inf} values where the percentage extrapolation is less than 20% will be reported. AUC_{0-inf} values where the percentage extrapolation is between 20 to 30% will be flagged, and included in the summary statistics and statistical analysis, whilst AUC_{0-inf} values where the percentage extrapolation is greater than 30% will be reported but excluded from summary statistics and statistical analysis.

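### The SAP excepts Part 2 Day 8 for %AUCextrap and CL/F but not for AUC0-inf, λz or t1/2, which is not reconciled with its own 30% extrapolation rule

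*SAP*

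**What the plan says.** **Parameter table, SAP 8.5.1.** The %AUCextrap and CL/F rows carry the exception "except for Part 2 Day 8". The AUC0-inf row ("AUC extrapolated to infinity, calculated using the formula" and so on) has none. The λz and t1/2 rows are qualified only by feasibility. The corresponding table in Protocol 8.3 has no Day 8 exception for %AUCextrap or CL/F, so the SAP introduced it.

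**Extrapolation rule, SAP 8.5.1.3.** AUC0-inf below 20% extrapolation is reported. AUC0-inf whose "percentage extrapolation is between 20 to 30% will be flagged" is still included. AUC0-inf whose "percentage extrapolation is greater than 30% will be reported but excluded from summary statistics and statistical analysis" is listed only.

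**Caution on Day 8, SAP 8.5.1.** "The PK sampling to 24 hours on Day 8 in Part 2 may not be sufficient for calculation of several" λz-dependent parameters. The same paragraph withholds values only when no terminal log-linear phase is seen.

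**Other conditions on λz.** SAP 8.5.1.2 requires at least three points and an adjusted R² of at least 0.7. It prefers a fitting period of at least two half-lives. A shorter period leads to a flag at the pharmacokineticist's discretion and a discussion in the CSR.

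**Output.** SAP 8.5.3 summarises all PK parameters by treatment apart from regression diagnostics. SAP Table 4 makes LOXO-305 with rifampin once a treatment of its own. SAP 8.5.3.1 limits the single-dose rifampin comparison to AUC0-24 and Cmax.

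**The concern.** Day 8 is the one LOXO-305 profile sampled to 24 h; the others run to 168 h. It is therefore where a limit on extrapolation matters most, and it is also the only profile for which the SAP does not ask for the percentage on which the limit depends. Excepting CL/F and %AUCextrap suggests an intention to drop the Day 8 parameters that depend on λz, with three rows missed, but the documents do not say so.

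If the table is programmed as written, a Day 8 AUC0-inf that is largely extrapolated could be tabulated beside Day 1 and Day 17 values that are almost entirely observed. A Day 8 half-life fitted over little more than one half-life could appear in the same table. A reader could then see an effect of a single rifampin dose on total exposure or half-life that the 24-h sampling was not designed to measure.

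**Working it through.** The documents give no expected extrapolation for Day 8, so there is no planned figure to reproduce.

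**Inputs**
- Last sample T: 24 h on Part 2 Day 8 and 168 h on the other profiles (Protocol 3.1; SAP 4.1 and 4.2).
- Half-life: "it appears to be approximately 18 hours" (Protocol 1.4.2). It comes from 0 to 8 h sampling in patients, and the protocol calls it uncertain. I assume a range of 8 to 30 h around it.
- tmax: about 2 h (Protocol 1.4.2), varied from 1 to 3 h.
- Assumed model: one compartment with first-order absorption. The absorption rate ka is solved from tmax = ln(ka/k)/(ka − k), with k = ln 2 / t1/2.

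**Extrapolated share**

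Share = (C_T/k) / (AUC0-T + C_T/k). Once absorption is over, this reduces to exp(−kT) / (1 − k/ka).

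At t1/2 = 18 h:
- k = 0.693/18 = 0.0385 per h, and tmax = 2 h gives ka ≈ 2.02 per h.
- exp(−0.0385 × 24) = 0.397.
- Share = 0.397 / (1 − 0.0385/2.02) = 0.397/0.981 = 40.5%.
- Varying tmax from 1 to 3 h gives 40.0% to 41.0%. Ignoring absorption gives 39.7%.

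| t1/2 (h) | Share extrapolated, 24-h sampling | Treatment under SAP 8.5.1.3 | Half-lives from tmax to 24 h |
|---|---|---|---|
| 8 | 13% | reported | 2.75 |
| 12 | 26% | flagged, included | 1.83 |
| 14 | 31% | excluded | 1.57 |
| 16 | 36% | excluded | 1.38 |
| 18 | 40% | excluded | 1.22 |
| 20 | 44% | excluded | 1.10 |
| 24 | 51% | excluded | 0.92 |
| 30 | 58% | excluded | 0.73 |

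The 20% limit is reached at a half-life of about 10.1 h and the 30% limit at about 13.5 h. Without absorption, the latter is 24 × ln 2 / ln(1/0.3) = 13.8 h. With 168-h sampling the share at 18 h is 0.16%, and the half-life must reach about 97 h before 30% is passed. Day 8 is therefore the only profile expected to breach the limit.

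**What that share means for AUC0-inf.** With C24 held fixed, the extrapolated part is proportional to the fitted half-life. A 30% error in that half-life moves a Day 8 AUC0-inf by 0.405 × 30% ≈ 12%.

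**λz and t1/2.** The longest window after tmax is 24 − 2 = 22 h, and 22/18 = 1.22 half-lives. A span of two half-lives fits only if the half-life is 22/2 = 11 h or less. The sampling times are redacted, so the actual fitting window cannot be known; 1.22 is an upper bound for a fit that starts after tmax.

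**Does another rule remove the values?** No. The log-linearity, three-point and R² conditions do not limit extrapolation, and a short span is flagged rather than excluded.

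**The case against.** The strongest reply is that SAP 8.5.1.3 has no Day 8 carve-out. It covers any AUC0-inf, and the percentage follows from AUC0-t and AUC0-inf, both of which the table defines. The exception can then be read as meaning that %AUCextrap is not a reported Day 8 parameter, with the 30% rule still in force. This stands as far as it goes. A reader might infer that the rule is disabled on Day 8, but the documents do not support that. They leave two passages unreconciled, and a programmer could follow either.

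A reader might also infer that the rule would have screened t1/2 and λz. It would not: SAP 8.5.1.3 screens AUC0-inf only, on every day and in both parts. The Day 8 half-life belongs under the two-half-life guidance, which has safeguards of its own: listed span ratio, points used and adjusted R², a possible flag, and a CSR discussion. These lessen the problem but do not keep the values out of the summary.

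A third tempting reading is that induction from the later rifampin doses invalidates the Day 8 tail. The samples end at 24 h, about when the second rifampin dose is due, so later induction does not enter them. An extrapolation from them estimates the single-dose course that the objective asks about. The weakness is the amount of extrapolation.

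Two further limits stand. The output shells are in a separate document that is not available here, so it cannot be confirmed that Day 8 AUC0-inf is tabulated. The 18 h half-life is soft: below about 13.5 h a typical Day 8 profile would be within the limit.

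**Conclusion.** The inconsistency is real and worth correcting, but its reach is modest. At the protocol's approximate half-life, a typical Day 8 AUC0-inf would be about 40% extrapolated. SAP 8.5.1.3 would exclude it, whereas the parameter table, taken literally, lets it through without producing the screening quantity. This rests on the one-compartment model and on a half-life above about 13.5 h.

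It would be wrong to conclude that the single-dose rifampin objective is compromised, since the listed Day 8 comparison uses AUC0-24 and Cmax only. The main effect is on the descriptive summary. There is a secondary route: the general model sentence and the example code in SAP 8.5.3.1 show no step that removes Day 8 from the AUC0-inf model. Run that way, the model would give an unplanned Day 8 ratio and let Day 8 values into the residual variance behind the Day 17 interval. The code is labelled as an example and its input dataset is not described, so this is a possibility to close off and not a stated plan.

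**What to change.** - In SAP 8.5.1, add "except for Part 2 Day 8" to the AUC0-inf, λz and t1/2 rows, to match %AUCextrap and CL/F.
- In SAP 8.5.3.1, state that the Part 2 AUC0-inf model uses Day 1 and Day 17 only.
- If Day 8 AUC0-inf is to be kept, determine %AUCextrap for it and apply the 30% exclusion explicitly. This alternative does not deal with Day 8 t1/2 and λz, which would still need a decision.

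The cost is three table entries, one sentence on the model, and matching edits to the shells. No data collection changes and no listed comparison is lost. The small downside is that Day 8 AUC0-inf and t1/2 are no longer summarised.

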8.5.1.2.1. Number of Data Points

At least 3 data points will be included in the regression analysis and preferably should not include C_{max} .

8.5.1.2.2. Goodness of Fit

When assessing terminal elimination phases, the adjusted coefficient of determination for exponential fit (R^2 adjusted) value will be used as a measure of the goodness of fit of the data points to the determined line.

Regression-based parameters (eg, AUC_{0-inf}, λ_z , $t_{1/2}$, and CL/F) will only be calculated if the R² adjusted value of the regression line is greater than or equal to 0.7.

8.5.1.2.3. Period of Estimation

The time period used for the estimation of apparent terminal elimination rate constant, where possible, will be over at least 2 half lives.

Where the terminal elimination rate constant is estimated over a time period of less than 2 half-lives, it will be flagged in the data listings at the discretion of the Pharmacokineticist, and the robustness of the value should be discussed in the CSR.

8.5.1.3. Calculation of AUC

The minimum requirement for the calculation of AUC will be the inclusion of at least 3 consecutive plasma concentrations above the lower limit of quantification (LLOQ), with at least one of these concentrations following C_{max} .

For any partial AUC determination (eg, AUC_{0-24}), nominal time will generally be used for the end of the interval. Actual times for partial AUC intervals may be used at the discretion of the pharmacokineticist.

 AUC_{0-inf} values where the percentage extrapolation is less than 20% will be reported. AUC_{0-inf} values where the percentage extrapolation is between 20 to 30% will be flagged, and included in the summary statistics and statistical analysis, whilst AUC_{0-inf} values where the percentage extrapolation is greater than 30% will be reported but excluded from summary statistics and statistical analysis.

8.5.1.4. Anomalous Values

If a value is considered to be anomalous due to being inconsistent with the expected PK profile, it may be appropriate to exclude this point from the PK analysis. However, the exclusion of data must have strong justification and will be documented in the raw data and the CSR.

Embedded BLQ values may be considered anomalous depending on the route of administration and the characteristics of the drug.

Subjects with positive predose values greater than 5% of Cmax may be excluded from the summary statistics and statistical analysis at the discretion of the Pharmacokineticist.

8.5.2. Presentation of Pharmacokinetic Data

8.5.2.1. Presentation Pharmacokinetic Plasma Drug Concentration Data

The following rules will be applied if there are values that are BLQ or if there are missing values (eg, no result [NR]) in plasma concentration data series to be summarized.

- For the calculation of summary statistics, BLQ values will be set to zero.
- If an embedded BLQ value is considered anomalous within the concentration-time profile, this value will be excluded from the summary statistics.
- Where there is NR, these will be set to missing.
- If there are less than 3 values in the data series, only the minimum, maximum and N will be presented. The other summary statistics will be denoted as not calculated (NC). BLQ is considered a value.
- If all the values are BLQ, then the arithmetic mean, arithmetic standard deviation (SD), median, minimum and maximum will be presented as zero, and the geometric mean and geometric coefficient of variation (CV) will be denoted as NC.
- If the value of the arithmetic mean or median is below the LLOQ, these values will be presented as zero and the geometric mean and geometric CV will be denoted as NC.

8.5.2.2. Presentation Pharmacokinetic Parameters

For the calculation of summary statistics of PK parameters, all NR and NC values in a data series will be set to missing.

The AUC values will be set to NC if they have been calculated using fewer than 3 concentrations, and/or 3 concentrations if the last is C_{max} .

8.5.3. Pharmacokinetic Statistical Methodology

All PK concentrations and parameters will be listed.

Summary tables, mean (+ SD) figures, overlaying individual figures, and individual figures by treatment and time postdose will be provided for plasma PK concentrations. All PK concentration figures will be produced on both linear and semi-logarithmic scales, with the exception of figures across all days, which will be produced on the linear scale only. The +SD bars will only be displayed on the linear scale.

Summary tables by treatment will be provided for all PK parameters, with the exception of diagnostic regression-related PK parameters. Summary statistics (n, Mean, SD, CV%, minimum, median, maximum, geometric mean [Geom Mean] and geometric CV% [Geom CV%]) will be calculated for plasma LOXO-305 PK parameters. Excluded subjects will be listed in the PK parameter tables, but will be excluded from the summary statistics and noted as such in the tables.

8.5.3.1. Statistical Analyses

A statistical analysis will be conducted to investigate the drug-drug interaction on the PK of LOXO-305 for AUC₀₋₂₄, AUC_{0-t}, AUC_{0-inf}, and C_{max} . The comparisons of interest are:

Study Part 1:

To access the impact of multiple oral doses of itraconazole on the single oral dose PK of LOXO-305 (AUC_{0-t}, AUC_{0-inf}, and C_{max})

• 200 mg itraconazole co-administered with 200 mg LOXO-305 (test treatment) vs 200 mg LOXO-305 alone (reference treatment).

Study Part 2:

To assess the effect of multiple oral doses of rifampin (strong CYP3A4 inducer) on the single oral dose PK of LOXO-305 (AUC_{0-t}, AUC_{0-inf}, and C_{max}) in healthy adult subjects

• 600 mg rifampin QD co-administered with 200 mg LOXO-305 (test treatment, Day 17) vs 200 mg LOXO-305 alone (reference treatment)

To assess the effect of a single oral dose of rifampin on the single oral dose PK of LOXO-305 (AUC₀₋₂₄, and C_{max})

• 600 mg rifampin once co-administered with 200 mg LOXO-305 (test treatment, Day 8) vs 200 mg LOXO-305 alone (reference treatment)

The ln-transformed³ PK parameters (AUC₀₋₂₄, AUC_{0-t}, AUC_{0-inf}, and C_{max}) will be analyzed using a mixed model.⁴ The model will include actual treatment as fixed effect, and subject as a random effect.

For each PK parameter separately, the least squares mean (LSM) for each treatment, difference in LSMs between the test and reference treatments, and corresponding 90% confidence interval (CI) will be calculated; these values will then be exponentiated to give the geometric least squares mean (GLSM), geometric mean ratios (GMR), and corresponding 90% CI.

Additionally, the pooled estimate (across all treatments) of the within-subject CV will be calculated, and residual plots will be produced to assess the adequacy of the model(s) fitted.

Examples of the SAS code that will be used are as follows:

Mixed Model Analysis

```
proc mixed data = <data in>;
by parcatln parcatl paramn param;
class trtan usubjid;
model lpk = trtan / cl residual ddfm = kr;
lsmeans trtan / cl pdiff = control('1') alpha = 0.1;
random intercept / subject = usubjid;
```

```
ods output lsmeans = <data out>;
  ods output diffs = <data out>;
  ods output covparms = <data out>;
run;
```

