1.5. Study Rationale

The objective of drug-drug interaction (DDI) studies is to determine whether potential interactions between an investigational drug and other drugs exist. Drug-drug interaction studies have an important role in drug development,⁶ and this study is being performed as part of the development program for LOXO-305.

In non-clinical studies, LOXO-305 was metabolized slowly by human microsomal fractions and hepatocytes. The low rates of metabolism in both these human in vitro systems suggest that LOXO-305 will have low clearance in humans. In vitro data with cloned expressed CYP enzymes and human liver microsomes indicate that CYP3A4 is the primary enzyme that metabolizes LOXO-305. It is also a substrate for direct glucuronidation and P-gp. Given the theoretical potential for CYP3A4 inhibitors or inducers to alter the PK of LOXO-305, a clinical drug interaction study is warranted to determine the extent of any interaction. This study is designed to determine the effect of CYP3A4 and P-gp inhibition by itraconazole and CYP3A4 induction and P-gp inhibition by rifampin on the PK of LOXO-305. Itraconazole is a strong CYP3A4 and P-gp inhibitor commonly used as a prototypical CYP3A4 inhibitor in DDI studies. Likewise, rifampin is a strong CYP3A4 inducer and is commonly used as a prototypical CYP3A4 inducer in DDI studies.⁶ Rifampin has also been shown to be an effective inhibitor of P-gp in the gut when administered as an acute single dose.

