As itraconazole capsules should be administered with a full meal to maximize its absorption, on Days 9 to 11 and 13 to 18, the dose of itraconazole will be administered alone at the actual time of the Day 1 LOXO-305 dose (\pm 1 hour), approximately 30 minutes after the start of a standard breakfast to maximize the inhibition potential. On Day 8, when itraconazole is administered BID, the morning dose will be administered alone at the actual time of the Day 1 LOXO-305 dose (\pm 1 hour), approximately 30 minutes after starting a standard breakfast, and the evening dose will be administered approximately 10 (\pm 1) hours after the morning dose, approximately 30 minutes after starting a standard evening meal. All meals should be entirely consumed within 30 minutes. On Day 12, to assess the DDI under the most sensitive conditions, both itraconazole and LOXO-305 will be administered in the fasted state (ie, following a fast of at least 10 hours prior to and 4 hours after dosing with itraconazole and LOXO-305).

Rifampin

The dose of rifampin selected for this study is 600 mg QD, which is the commonly used clinical dose level. Rifampin will be dosed QD for 16 days (ie, Days 8 to 23), with LOXO-305 co-administered on the first and tenth day after the start of rifampin dosing (ie, Days 8 and 17, respectively). As per literature, an acute dose of rifampin inhibits P-gp-mediated transport while chronic dosing strongly induces CYP3A enzymes and P-gp.¹¹ Therefore, the acute (transporter) effect of a single dose of rifampin on the single-dose PK of LOXO-305 will be assessed to maximize the ability to observe small differences in PK. Sampling up to 24 hours will be sufficient to evaluate the inhibitory effects as P-gp acts mostly in the gut (absorption/distribution phases). Rifampin dosing alone will then be continued QD to assess its induction potential on LOXO-305. The half-life of rifampin is approximately 3 hours following a 600-mg oral dose;⁸ however, the time required to produce maximum enzyme induction is substantially longer for the synthesis of new enzymes. The timeframe from maximum induction by rifampin has been estimated at a minimum of 5 days of 600-mg QD dosing.⁹ In most DDI studies, oral rifampin is typically administered as a 600-mg QD dose for 4 to 18 days.¹² Dosing will continue until Day 23 to maintain induction throughout the PK sampling time.

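### Does Part 2 need a Day 17 versus Day 8 comparison to separate rifampin's induction effect from its acute P-gp inhibition?

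*SAP*

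**What the plan says.** SAP Section 8.5.3.1 lists two Part 2 comparisons, both against LOXO-305 alone on Day 1:

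- Multiple-dose rifampin: "600 mg rifampin QD co-administered with 200 mg LOXO-305 (test treatment, Day 17) vs 200 mg LOXO-305 alone (reference treatment", for AUC0-t, AUC0-inf and Cmax.
- Single-dose rifampin: "600 mg rifampin once co-administered with 200 mg LOXO-305 (test treatment, Day 8) vs 200 mg LOXO-305 alone (reference treatment", for AUC0-24 and Cmax.

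The example code asks for differences from treatment 1 only: "lsmeans trtan / cl pdiff = control('1') alpha = 0.1". SAP Section 8.5.1 defines AUC0-24 "for Day 1 and Day 8 of Part 2 PK only".

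Protocol Section 1.5 says the study is to determine the effect of "CYP3A4 induction and P-gp inhibition by rifampin on the PK of LOXO-305". Protocol Section 3.3 states that "an acute dose of rifampin inhibits P-gp-mediated transport while chronic dosing strongly induces CYP3A enzymes and P-gp" and, after describing Day 8, adds: "Rifampin dosing alone will then be continued QD to assess its induction potential on LOXO-305".

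The primary objectives (Protocol Section 2.1, SAP Section 2.1) name the effect of multiple rifampin doses and the effect of a single rifampin dose as two separate items.

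**The concern.** LOXO-305 is a P-gp substrate, and it is taken together with rifampin on both Day 8 and Day 17. If the Day 17 rifampin dose inhibits gut P-gp as the Day 8 dose is expected to, Day 17/Day 1 is an induction ratio multiplied by an acute inhibition ratio. Day 8 carries the acute part before induction has developed, so Day 17/Day 8 in the same subjects seems to be the cleaner measure of induction. The plan does not list that contrast and provides no matching AUC for it.

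At stake would be an understated induction effect. With a true induction ratio of 0.30 and an acute ratio of 1.25, Day 17/Day 1 would show a 62.5% fall in exposure instead of 70%, and no confidence interval would be produced for the induction component.

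**Working it through.** **1. Objectives against contrasts.**

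| Primary objective | Planned contrast |
|---|---|
| Effect of multiple-dose rifampin on LOXO-305 PK | Day 17 vs Day 1: AUC0-t, AUC0-inf, Cmax |
| Effect of single-dose rifampin on LOXO-305 PK | Day 8 vs Day 1: AUC0-24, Cmax |

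The match is one for one. No objective asks for a mechanism-specific induction ratio. Protocol Section 1.5 speaks of determining the effects on PK, not of separating them numerically.

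**2. What Day 17/Day 8 would measure.** Protocol Section 3.3 sets an acute dose, which inhibits P-gp, against chronic dosing, which induces CYP3A and P-gp. Two things follow. By Day 17 P-gp itself is induced, so Day 17/Day 8 combines CYP3A and P-gp induction. Cancelling the acute component would also require equal acute inhibition on both days, although the amount of transporter is expected to have changed. The protocol does not say that the tenth daily dose still inhibits P-gp. That is plausible, but it is an inference.

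**3. Size of the mixing.** The documents give no acute effect, induction effect or within-subject CV, so these values are assumptions. Write A for the acute ratio and I for the induction ratio; then Day 17/Day 1 = A × I.

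- I = 0.30 with A = 1.00, 1.10, 1.25, 1.50 gives 0.30, 0.33, 0.375, 0.45.
- I = 0.50 with the same A gives 0.50, 0.55, 0.625, 0.75.

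**4. Error of the suggested replacement.** Day 8 is sampled only to 24 hours, so the like-for-like AUC would be AUC0-24. Take a one-compartment model with half-life 18 h (Protocol Section 1.4.2, itself described as uncertain), assumed ka = 1.5/h, and induction acting on systemic clearance. The share of AUC0-inf that falls in the first 24 h is

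f = [(1 − e^(−24k))/k − (1 − e^(−24ka))/ka] / (1/k − 1/ka), with k = ln 2 / half-life.

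- Without induction: half-life 18 h, k = 0.0385, f = 0.593.
- I = 0.30: half-life 5.4 h, k = 0.128, f = 0.950. AUC0-24 ratio = 0.30 × 0.950/0.593 = 0.48.
- I = 0.50: half-life 9 h, k = 0.077, f = 0.834. AUC0-24 ratio = 0.50 × 0.834/0.593 = 0.70.

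Varying ka from 0.7 to 3/h moves these only to 0.48–0.49 and 0.70–0.71.

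| True AUC0-inf ratio | Day 17/Day 8, AUC0-24 | Day 17/Day 1, AUC0-inf, A = 1.10 | A = 1.25 | A = 1.50 |
|---|---|---|---|---|
| 0.30 | 0.48 | 0.33 | 0.375 | 0.45 |
| 0.50 | 0.70 | 0.55 | 0.625 | 0.75 |

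The planned contrast is closer to the true ratio in five of the six cells. The two are equally far off at A = 0.48/0.30 = 1.6 and A = 0.70/0.50 = 1.4.

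**5. Is the contrast blocked?** No. Cmax is derived on all three days and the SAP reports a least squares mean for each treatment, so the Day 17/Day 8 Cmax ratio follows from planned output; only its interval is not printed. Day 17 is sampled to 168 h. The sampling times are not visible, but the PK sample counts in Protocol Appendix 3 (40 in Part 1, 53 in Part 2) fit 20 + 13 + 20, that is, a full Day 17 profile. SAP Section 8.5.1 allows additional PK parameters and SAP Section 1 allows supplementary analyses identified in the study report.

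**The case for a change.** The best case for the extra comparison is that the protocol itself gives continued rifampin dosing an induction purpose. All three occasions are measured in the same subjects, and no new samples are needed. Precision would match that of the planned contrasts: for n = 12 and an assumed CV of 30%, the 90% interval is the ratio multiplied or divided by about 1.23 in a three-treatment model. In a simulation with A = 1.25 and I = 0.30, the 90% interval for Day 17/Day 1 covered 0.30 in 44% of runs, against 89% for Day 17/Day 8. In an open-label study, adding the contrast after Day 8 results are known would be data-driven.

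Part of this stands. Day 17/Day 1 is a net effect, and if Day 8 shows an increase it should not be read as a pure induction ratio. The omissions are also real. But the simulation treats the induction ratio as identical on every exposure measure and the acute component as equal on both days. It therefore leaves out the truncation in step 4 and the P-gp induction in step 2. Truncation would matter less if much of the induction acted on first-pass loss rather than systemic clearance, but the documents do not settle this. Even the case for the contrast keeps Day 17 versus Day 1 as the primary estimate.

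**Conclusion.** The concern does not hold. The planned contrasts estimate the two stated rifampin objectives, and no planned number, rule or conclusion is wrong. The Day 17 versus Day 8 comparison would be an optional supportive analysis with its own problems. It combines CYP3A and P-gp induction, needs equal acute inhibition on both days, and on AUC0-24 would read about 0.48 for a true 0.30 and about 0.70 for a true 0.50. That is further from the truth than the planned AUC0-inf ratio unless the acute effect exceeds roughly 1.6 or 1.4 respectively.

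These figures assume one-compartment kinetics, the preliminary 18-hour half-life and induction of systemic clearance. The mixing itself rests on acute ratios that the documents do not give, and it vanishes if the acute ratio is 1. The conclusion that the contrasts match the objectives depends on none of these assumptions.
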